c) Document the risks associated with the study. When the research participant is a patient, document the risks as compared to the usual care that the patient would receive. If the risks vary according to the group to which patients are assigned, document the risks for each group.

In CG study:

There are minimal risks to this study. Some participants may not enjoy CG or the neuropsychological testing. If so, he/she will be excused from participation. Participants will be reminded about their right to withdraw from the study at any point.

In NCP study:

The discomfort arising from auditory stimulation should not exceed that associated with playing a video game. Sound intensity will not exceed 80dB, which is well below the threshold of pain even under repetitive-stimulation conditions. Preparation of EEG recording sometimes requires skin abrasion and cleansing (with alcohol pads and scrubs) to ensure a good connection between the EEG electrode and the scalp. Participants may experience mild skin irritation and/or discomfort from this skin preparation. For example, hair can get tangled and pulled when

abrading the skin with a wooden dowel. Participants will be encouraged to tell the experimenter whether they are experiencing any discomfort. To minimize communication of viruses and bacteria, the elastic cap and electrodes are placed in an intermediate-level surface disinfectant that kills TB, HepB, HepC, HIV, fungi and other viruses and bacteria within 3 minutes. The risks are about the same as in hair salon. The risks of being connected to the EEG recording device are minimal. The cap contains a ground electrode to prevent the buildup of excessive static charge. The amplifier is battery powered and cannot be charged and attached to the participant at the same time. The cap can be easily removed should the need arise. The RA administering the NCP have been trained in proper application of the electrodes and the cap, this will reduce the likelihood of a pressure headache from an ill-fitting cap. She has also been trained in removal of loose electrodes to reduce the discomfort of removing adhesive material from the skin.

An adverse event (AE) is any untoward medical occurrence in a study participant which does not necessarily have a causal relationship with the study's intervention. An AE can therefore be any unfavorable and unintended sign, symptom, or disease temporally associated with the use of an investigational study intervention, whether or not related to the investigational study intervention. Worsening of a pre-existing condition is also considered an AE. An adverse device reaction (ADR) is an event related to the use of the NCP. During each visit, information on AE and ADR will be gathered and documented accordingly (**Appendix 16: Case Report Form**). Whenever an AEs or ADR is registered, the research assistant will share this information with the Principal Investigator within 24-488 hours from the incident. The severity of the event will be graded by the Principal Investigator as mild, moderate, severe, or life threatening and its causality will be assessed as probably related, possibly related, unlikely to be related, or not related to the device. The Principal Investigator will decide if study disruption is required. All incidents and decisions taken will be notified to the Study Partner, SDM, and Ethics Board, at the earliest opportunity (within 72 hours from the incident).

d) Will participation in this study affect alternatives for the future care of the participant?

There is no direct impact to the future care of the participants.

e) Will the management of the participant's condition be prolonged or delayed as a result of the research?

Yes No Not applicable

If yes, describe any risks associated with prolongation or delay (e.g. washout period, withholding of treatment or absence of treatment).

f) Are there any standard therapies, diagnostic procedures or information to be withheld from participants for the purpose of the study?

Yes No Not applicable

If yes, describe the risks and benefits to the participants. In the case of risks to the research participant that go beyond those of usual care, please provide the justification for exposing the research participants to these additional risks.

g) Are there any restrictions being placed on the study's participants?

Yes No

If yes, please explain

h) Are placebos being used?

Yes No

If yes, please explain and provide justification according to the Tri-Council Policy Statement (see guidelines).

i) Does this study involve any deception of, or withholding information from study participants?

Yes No

If yes, please explain the justification for employing these techniques (see guidelines for conditions under which these techniques may be used).

j) Outline the criteria for the early withdrawal of research participant(s).

Participants are free to withdraw at any point, without need for explanation. Consent will be reassessed every 6 months. Additionally, if any dissent behavior is observed during the testing session, the session will be suspended and a new session will be rescheduled. The research team will cover parking costs each time they need to return. If this is repeated three times, the PWD will be withdrawn from the study. SDMs will be informed of this decision

k) Describe any possible benefits to the research participants as a result of their participation in the research study.

There are no direct benefits, though patients may enjoy the research process. The main benefit is to the scientific community by developing generalized knowledge of brain functioning. If during the trial, a participant progresses to MCI or dementia, the research coordinator will advise them and their study partners to notify their family doctor. A report including their scores in the cognitive tests will be shared with them, if requested. Additionally, participants may request a report of study results. This is included in the consent form and will be enhanced during the consent review process at the baseline session. Participants may request to the RA a report of study results at any moment. Requests can be done in person, over the phone, or by e-mail. Reports will include the results in the neuropsychological tests and total score in the FAQ, specifying that the data corresponds to a research project. It will not include any diagnostic interpretation. For a template of the report, please **see Appendix 17: Results report template**. Study partners and SDMs may also ask for a report of the results. However, they will only be shared with them after confirming assent of the main participant for sharing their results with them (**Appendix 18: assent for sharing results**). Because the report will contain personal identifiers, they will only be given in-person at the Bruyère Hospital by the RA to the main participant and/or study partner and/or SDM.

19. CONFIDENTIALITY (See Guidelines)

a) List the types of records containing personal information that will be accessed in the course of this study. Please outline the health information custodian's requirements for access, and whether the requirements have been met and access has been approved.

The following records will contain personal information:

1. Consent forms: will be printed, and the email will be deleted at the earliest opportunity. The printed versions will be kept inside a filing cabinet in the RA's office located at BRI.
2. Master Code: will be safely kept under lock, in a cabinet in the RA's office at BRI (separated from the consent forms). A digital copy will also be kept in the BRI computer, using a password-protected Excel file.

Every other document (e.g., CG results, NCP outputs, Case Report Forms, MoCA, NPS battery, FAQ, and GPCOG results) will use Study ID and will have no personal identifiers. Every paper document will use Study ID and kept in a filing cabinet at the RA's BRI office. Every electronic document will use Study ID and will be shared between the team members using password-protected files. The Cognigram software automatically flows data to the Cogstate database. The data will be de-identified: Study ID, age, years of education and gender will be included. Cogstate standard research contracts allow Cogstate to use de-identified data for their own research. A research agreement with Cogstate will be signed and shared with the REB prior initiating the study. The Cogstate application is HTML web-based software with both authentication and authorization rules based off of NIST guidelines. Cogstate currently uses Microsoft Azure HIPAA compliant cloud based servers/services which include appropriate safeguards for data privacy. They have password protected access controls based on authorized user roles. Cogstate maintain the entire database with geo-redundant back-ups as they have not needed to archive any data at the moment, however, they are required to maintain the records for 6 years should they archive in the future.

Regarding the NeuroCatch software, the data captured is kept locally on the laptop used. This laptop will be property of our research team, will be password-protected, and will not leave the Bruyère Hospital. No one other than our research team will have access to this data. To further protect the participant's privacy, the files will only include study ID and will not have any personal identifiers.

b) Describe the methods that will be employed to maintain confidentiality during the time that research data sets contain personal identifiers. If different data collection mediums are being used (e.g. paper forms, audiotapes, video tapes, local computer databases, web-based database), describe the security measures that will be used for each medium.

As mentioned before, only the Consent Forms and Master list will contain personal identifiers. All other study's data will use Study ID, without any personal identifier. However, to further ensure the participants' confidentiality, all data will be kept inside the RA's office located at BRI on in password-protected Excel files in the RA's computer.

c) Describe how and when the data will be encoded to remove all personal identifiers from the data collected during the course of the study.

As soon as the Consent Form is received, and therefore the participant is confirmed as part of the study, the participant will be identified using a random ID. The RA will create a master code list, with the demographic information of each participant and the randomized ID given. This list will be kept separate from the study's outputs, and will be under lock in a BRI office. Throughout the study, the project's data will be collected using Study ID with no personal identifiers.

d) If data containing personal identifiers will not be encoded at the earliest opportunity, please justify.

_____ Not applicable

e) Please indicate where the code-list will be stored and when it will be destroyed. Please note that the Health Records Departments of some facilities offer a service to store code-lists over long periods of time (e.g. 25 years). Master list will be stored in a password-protected Excel file in the RA's computer located at the BRI office, separate from the Study's data. It will be deleted after seven years after the completion of the study.

f) If data containing personal identifiers will be transferred to another facility, please justify. In addition, please provide documentation that ensures the confidentiality of this information at the receiving facility (see guidelines for specific requirements). The transfer of information to another facility should also be described in the information/consent form.

Not applicable. Electronic database with study's outputs will be shared with Carleton engineering team, for analysis. However, this database will be de-identified. File will be shared using encrypted files to further ensure participants confidentiality. Cognigram software also flows data to Cogstate, however the data does not contain personal identifiers. NCP outputs will be shared with Carleton engineering team for analysis. The data will be de-identified, and shared through encrypted files.

g) Will project research staff be required to sign a Pledge of Confidentiality to comply with the policy and procedures of the research site facility?

Yes No Not applicable

If No or Not Applicable, please explain.

h) Please indicate how long data will be kept, how it will before being destroyed and what measures are in place to ensure on-going confidentiality of the dataset. Data will be kept for 7 years post-completion of the study, and will be destroyed after this time. The master list will be in a password-protected Excel file at the RA's computer located in a BRI office, separate from the output database and study's outcomes.

Not applicable

i) If your study involves collection of any biological specimens (e.g., blood, tissue, urine, etc), please indicate whether specimens are de-identified, where specimens will be stored, for how long and how they will be destroyed. * *If long term storage of specimens is planned, you must complete the "Genetic Addendum".*

Not applicable

20. MONITORING (See Guidelines)

a) Is there a plan to monitor the study (e.g. internal audits or sponsor-initiated site visits)?

Yes No

If yes, describe briefly and append the plan as an appendix.

b) For sponsor-initiated research (e.g. drug trials, medical devices) is there a data safety monitoring board in place?

Yes No Not applicable

If yes, describe the composition of the board's members. Are the board's members independent of the study and/or sponsor?

c) Are there interim analyses planned?

Yes No

If yes, describe briefly.

d) Describe the stopping rules for the study.

Not applicable

21. PUBLICATION AND DISSEMINATION OF RESULTS (See Guidelines)

a) If this study is funded, will the investigator(s) require the approval of the sponsor(s) before publication or dissemination of the results? Yes No
 Not applicable

If yes, please explain

b) Please describe the plan for publication and other dissemination of the study's results.

Presentations will be made at local and international conferences focused on dementia. Submissions to suitable clinical journals may also ensue.

c) Will a summary of the results be available in multiple languages?

English Yes No

French Yes No

Other Yes No If yes, specify _____

b) Please indicate who will cover the costs of treatment not covered by the provincial health plan in case of injury directly resulting from participation in a research study (e.g. sponsor, research facility or university).

Injury directly resulting from participating in this study is not expected.

24. POTENTIAL CONFLICTS OF INTEREST (See Guidelines)

a) Please indicate whether the Principal Investigator, Responsible Site Investigator or any Co-Investigators or other research staff involved in this research study or any member of their immediate family:

i) function as an advisor, employee, officer, director or consultant for the study sponsor?

Yes No

ii) have direct or indirect financial interest in the sponsoring corporation (e.g. stocks) drug, device or technology employed (e.g. patents) in this research study?

Yes No

iii) receive an honorarium or other financial benefits from the sponsor (apart from fee for service or regular salary)?

Yes No

iv) are receiving incentives to recruit research participants for this study?

Yes No

If the answer is yes to any of the above questions, append a letter detailing these activities. Please include a description of all conflicts of interest (actual, apparent, perceived, or potential) relating to this project.

b) Does this study comply with the current “conflict of interest” policies of the research site facility?

Yes No Not applicable

If no or not applicable, please explain.

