Appendix 1 - List of Investigators and Institutions

Application No. 281621

Date: 29 May 2018

Investigators; Names and addresses of Institutions
[name], Principal Investigator Elisabeth Bruyère Hospital [name]

10. STUDY SUMMARY/ABSTRACT (See Guidelines)

This summary must be suitable for lay audience (approximately 200 words). Please note that this is not a substitute for the full protocol, and do not refer the reader to sections of an attached protocol.

This research project will test two new computerized technologies in the detection of brain changes related to Mild Cognitive Impairment (MCI) and dementia due to Alzheimer's disease. These technologies are:

1) Computerized cognitive battery: Cognigram (CG) (*Appendix 1: Cognigram*)

Computerized assessments have multiple advantages for the early detection of subtle changes in cognition in older adults. One of their main advantages is their higher precision when measuring accuracy and speed of responses, compared to pencil-and-paper tests. They also allow a greater reliability in measures, as tests are given in a standardized format without the interference of an evaluator [1]. Finally, by including automatized instructions and reports, they are suitable for off-site or long-distance use.

The present study aims to validate the Cognigram™ (CG) [2] computerized cognitive tool (*Appendix 1: Cognigram*), in a prospective and longitudinal fashion, determining if changes in the CG scores over 3, 6, 9, and 12 months, can predict progression to dementia at 1-year, 2-years, and 3-years, for patients with Mild Cognitive Impairment (MCI).

For the purpose of this project, a total sample of 30 MCI and their study partners, and 30 cognitively normal subjects (CN), will be recruited. Study partners of MCI subjects will answer the functional questionnaire and the cognitive questionnaire required for defining the clinical status of participants. It is mandatory for MCI participants to have a study partner available in order to participate in this study.

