The participants will undergo CG and Montreal Cognitive Assessment (MoCA) (*Appendix 2: MoCA*) testing sessions at baseline, 3-months, 6-months, 9-months, and 12-months. The capacities for predicting clinical longitudinal outcomes (i.e., reversion to normal cognition, significant decline within MCI spectrum, or progression to dementia) of CG and MoCA will be compared. The clinical outcome will be assessed using a Neuropsychological battery, a functional assessment and a brief cognitive questionnaire at baseline, 12-months, 24-months and 36-months. It is expected that changes in CG scores will be sensitive to cognitive decline, allowing an early prediction of progression of the cognitive impairment.

2) The NeuroCatch™ Platform (NCP) (*Appendix 14: NCP*)

Event-related potentials (ERP) are non-invasive, low-cost, electrophysiological methods that allow recording of the electrical activity of the brain *in vivo* through an Electroencephalogram (EGG). They are free from cultural and educational influence and can provide insights into the cognitive processes (Jiang et al., 2015). ERP could enable us to detect brain changes and determine the prognosis of MCI subjects [16].

The NCP (*Appendix 14: NCP*), an investigational medical device system developed by NeuroCatch Inc., consists of an EEG software and hardware that captures brain health information. It offers a quick (i.e., 10 minutes for EEG preparation and 6 minutes for each task of EEG recording), simple (i.e., includes only 8 electrodes), and easy-to-use solution (i.e., includes a computerized software that automatically analyzes data and outputs graphs in less than 1 minute) for the acquisition of EEG and ERP.

For the purpose of this project, a total sample of 30 MCI and their study partners, and 30 cognitively normal (CN) subjects will be recruited. The participants will undergo NCP (*Appendix 14: NCP*) and MoCA (*Appendix 2: MoCA*) testing sessions at baseline, 6-months, 12-months, 24-months, and 36-months. The capacities for predicting clinical outcomes (i.e., reversion to normal cognition, significant decline within MCI spectrum, or progression to dementia) of the NCP and MoCA tests will be

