On the other hand, research and medicine is moving away from behavioral responses to assess brain health (e.g. verbal responses, reaction time, etc.) and are moving toward more neuroimaging focused measures. Biological tests could enable us to detect pre-dementia and determine the prognosis of MCI subjects [16]. A promising biological test is EEG/ERP. Our group has previously shown group differences in ERPs for patients with MCI and CN [17, 18]. Other studies have reported promising ERP markers of pre-dementia [15,19, 20,] and progression of MCI to dementia [21]. However, ERP can be complex to process and labor-intensive, limiting its value in the clinical setting [22]. For example, the usual time for an ERP series measuring multiple cognitive domains typically lasts 1 hour, another 25 minutes for applying the EEG cap and ensuring all electrodes are connected, and some 30 minutes per paradigm (x2-3 paradigms).

The NeuroCatch™ Platform (NCP) offers key competitive advantages compared to other EEG platforms, having a rapid test time with automated processing, analysis and results display – benefitting patients and clinicians being significantly easier to use than current EEG systems, and it alleviates training and ramp up costs amongst EEG users. In this study, we will use the NPC to explore for ERPs that could predict progression to dementia in patients with MCI. The present study will make an initial assessment of the capacity of the NCP to detect cognitive decline and predict conversion to dementia in patients with MCI.

Hypotheses:

In Cognigram, we hypothesize that the following will occur:

- i. Significant differences in the CG scores at baseline will be found between MCI and CN groups
- ii. MCI subjects will show greater longitudinal changes than the CN subjects
- iii. Intra-individual Significant longitudinal changes in the CG performances at 3 and/or 6 months and/or 9 months and/or 12 months, will relate to the prospective clinical outcome at 12-months, and/or 24-months, and/or 36-months.
- iv. The CG will show a higher sensitivity in detecting cognitive changes, and a higher predictive power of longitudinal clinical outcome than the pencil-and-paper MoCA test.

In NeuroCatch, we hypothesize that the following will occur:

- I. Significant differences in the ERP parameters (amplitude and latency of ERPs such as N100, N400, P300) at baseline will be found between MCI and CN groups

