- II. MCI subjects will show greater longitudinal changes in ERP parameters than the CN subjects
- III. Intra-individual significant longitudinal changes in ERP parameters at 6 months and/or 12 months and/or 24 months, will relate to the prospective clinical outcome at 12-months, and/or 24-months, and/or 36-months.
- IV. The NCP will show a higher sensitivity in detecting cognitive changes, and a higher predictive power of longitudinal clinical outcome than the pencil-and-paper MoCA test.

b) Objectives of the project:

The objectives of the project are as follows:

- i. To discriminate CG longitudinal changes related to neural damage from normal variations in cognitively normal (CN) older adults
- ii. To determine if CG baseline score is related to the clinical outcome at 12-months, 24-months, and 36-months
- iii. To determine if intra-individual CG changes at 3, 6, 9, and 12 months, are related to the clinical outcome at 12-months, 24-months, and 36-months.
- iv. To compare the powers of CG and MoCA for predicting longitudinal clinical outcomes.
- v. To discriminate ERP longitudinal changes (e.g., changes in N100, N400, P300 amplitudes and latencies) related to neural damage from normal variations in cognitively normal (CN) older adults.
- vi. To determine if ERP baseline parameters (e.g. amplitude of N100, N400, P300) is related to the clinical outcome at 12-months, 24-months, and 36-months
- vii. To determine if intra-individual changes in ERP parameters at 6, 12, and 24 months, are related to the clinical outcome at 12-months, 24-months, and 36-months.
- viii. To compare the powers of NCP and MoCA for predicting longitudinal clinical outcomes.

c) Clinical relevance of the project:

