Prospective longitudinal validation, if demonstrated, would greatly increase confidence in using CG and NCP in a clinical setting for the assessment of MCI patients and would allow early prediction of future clinical outcomes. This could help to develop preventive therapeutic strategies, while providing additional time for patients and their families to prepare for the future (e.g., financial arrangements, treatment options, and community services). CG and NCP would be of greatest use in primary care, where multiple constraints make cognitive assessments problematic (e.g., lack of time to perform cognitive testing, and lack of access to expensive neuropsychological testing not covered by OHIP) and EEG/ERP assessments prohibitive (e.g., lack of time to perform EEG, lack of access to trained experts for analyzing and interpreting the results of the EEG/ERP).

12. DESCRIPTION OF METHODS AND PROCEDURES (See Guidelines)

a) Study Design and Methodology:

The Study will have a longitudinal design, with a total duration of 3 years. For a summary scheme of the study design, please see **Appendix 3: Project's Workflow**. All processes involved in the study will be performed at the Bruyère Memory Program. The research team will cover parking costs, if required.

- Participants

Both projects (CG and NCP) will include 30 participants with MCI and their Study partners and 30 CN subjects.

The projects will be offered as parallel studies, meaning that we will invite potential participants to participate in the CG and/or NCP studies. By merging both projects, we will reduce the load (e.g., testing sessions and visits to the clinic) to individuals interested in participating in both studies. Merging is possible given that the same populations (i.e. MCI and CN), neuropsychological battery, functional questionnaire, and brief cognitive complaints questionnaire are needed in both projects. The main objective of both studies is the same: testing computerized technologies in the prediction of the longitudinal outcomes of MCI subjects.

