-Follow-up Clinical Outcomes: The clinical outcomes of participants will be determined at the 12-months, 24-months, and 36-months. For this, participants will undergo the NPS battery (50-60 minutes) and answer the GPCOG (5 minutes). Participants will be given a 10 minutes break halfway through the NPS assessment, after which testing will be resumed. The FAQ and GPCOG will also be administered to the Study Partners of MCI subjects preferably in person but if not, by phone. In the case of the 12-months session, the NPS battery will be administered to the participants after finishing the CG testing

session, leaving a 10 minute break in between. The same RA (if possible) will perform all longitudinal assessments, to ensure consistency. The Neuropsychological battery, FAQ, and GPCOG outputs will be shared (using Study ID) with a Clinical Panel consisting of two physicians and two psychologists, for determining the Clinical Status of the participants. The panel will be blind to CG and MoCA results. The following clinical outcomes will be considered:

- a) Stable normal cognition (for CN subjects)
- b) Reversion to normal cognition (for MCI subjects)
- b) Conversion to MCI (for CN subjects)
- b) Stable MCI (for MCI subjects)
- c) Cognitive decline inside the MCI spectrum (for MCI subjects)
- d) Conversion to dementia

**For the longer sessions, in the case of intense fatigue in participant and incapacity to continue with the testing, we will interrupt the testing and ask them to return another day to complete the session.*

- Material
1. **Cognigram™ (CG):** is a validated, computerized battery of cognitive tasks based on card games, developed by Cogstate Ltd. This technology includes four tasks, with a total duration of 10-15 minutes. The subject is asked to answer each task by pressing either 'D' or 'K' keyboard buttons. The technology supports the measurement of attention/vigilance, processing speed, concentration, visual working memory and visual recognition memory. The software will run on a computer supplied by the Bruyère Research Institute, in a private test room. The RA will be present during the testing session, reading out loud the batteries standardized instructions and doing the practice trials with the participants. After the practice trials, the RA will not give any feedback or support. For more information see **Appendix 1: Cognigram**.

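### The Cognigram (CG) aim counts 12-month change as predicting a 12-month outcome measured in the same session; that pair is concurrent, and the NeuroCatch (NCP) wording does not exclude similar pairs

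*Protocol*

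**What the plan says.** **CG.** The study summary (Section 10) states the aim as whether "changes in the CG scores over 3, 6, 9, and 12 months, can predict progression to dementia at 1-year", then continues to two and three years. Hypothesis iii (Section 11a) expects that change at 3, 6, "9 months and/or 12 months, will relate to the prospective clinical outcome at 12-months" and at the later outcome visits. Objective iii (Section 11b) is "To determine if intra-individual CG changes at 3, 6, 9, and 12 months, are related to the clinical outcome at 12-months" and at 24 and 36 months.

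**Timing of the 12-month CG and outcome.** Section 12a (CG, follow-up clinical outcomes) says: "In the case of the 12-months session, the NPS battery will be administered to the participants after finishing the CG testing" session, with a break between. The visit table for the CG-only option shows the same order at Visit 5. The clinical panel assigns status from that battery and the questionnaires.

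**NCP.** Hypothesis III expects that event-related potential (ERP) change at 6, "12 months and/or 24 months, will relate to the prospective clinical outcome at 12-months, and/or 24-months" and at 36 months. Objective vii asks whether "intra-individual changes in ERP parameters at 6, 12, and 24 months, are related to the clinical outcome at 12-months" and at the two later outcome visits. NCP and the battery share the 12-, 24- and 36-month visits.

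**Stated use.** For CG, Section 10 says: "It is expected that changes in CG scores will be sensitive to cognitive decline, allowing an early prediction of progression of the cognitive impairment". Section 11c says that validation of both tools "would allow early prediction of future clinical outcomes", leaving patients and families more time to prepare.

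**The concern.** A prediction claim needs the predictor to be known before the outcome. CG change to 12 months is complete only at the 12-month visit, and the battery that determines 12-month status follows in the same sitting. An association between the two shows that CG tracks present status. It does not show that CG would have given warning.

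The protocol itself treats detecting decline and predicting conversion as separate aims (end of the rationale in Section 11a), so the label matters. As worded, a strong 12/12 association could be reported as meeting the prediction aim, and the clinical case in Section 11c rests on lead time. The comparison of predictive power with MoCA (objectives iv and viii) has the same weakness if same-visit pairs are included, because MoCA opens the same sessions.

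**Working it through.** The protocol gives no figure to reproduce on this point. The check lists every pairing of change visit and outcome visit that the text allows, and takes lead time = outcome month − change month.

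**CG.** Change visits 3, 6, 9 and 12 and outcome visits 12, 24 and 36 (Section 10; hypothesis iii; objective iii) give 4 × 3 = 12 pairs. Lead time in months:

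| CG change to | Outcome 12 | Outcome 24 | Outcome 36 |
|---|---|---|---|
| 3 | 9 | 21 | 33 |
| 6 | 6 | 18 | 30 |
| 9 | 3 | 15 | 27 |
| 12 | **0** | 12 | 24 |

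Eleven pairs have positive lead time, one has none and none is reversed. The zero pair is 1 of 12 overall and 1 of the 4 in the 12-month column. Four change times cannot be matched one to one with three outcome times, so no one-to-one reading of the CG lists removes it.

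**NCP.** Change visits 6, 12 and 24 and outcome visits 12, 24 and 36 (hypothesis III; objective vii) can be read in two ways.

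- Matched in order: 6 to 12, 12 to 24 and 24 to 36, with lead times of 6, 12 and 12 months. All are properly ordered.
- Fully crossed, 3 × 3 = 9 pairs:

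| ERP change to | Outcome 12 | Outcome 24 | Outcome 36 |
|---|---|---|---|
| 6 | 6 | 18 | 30 |
| 12 | **0** | 12 | 24 |
| 24 | −12 | **0** | 12 |

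Six pairs are lagged, two are same-visit (12/12 and 24/24) and one is reversed. The text does not say which reading applies. The times are joined by and/or in hypothesis III and simply listed in objective vii, and neither says that the lists are matched in order.

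**After the fix.** Requiring lead time above zero leaves 11 CG pairs, and 6 NCP pairs if the lists are crossed.

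**The case against.** The best reply is that the operative wording is mild. Section 10 is a lay summary. Hypothesis iii speaks of a relation to a prospective outcome, and objective iii only of a relation. The analysis plan in Section 12c is exploratory and includes cross-sectional discrimination. No passage says that the 12/12 result will be reported as lead time. Part of this stands: a 12/12 association is legitimate evidence of detection, and objective iii can accommodate it under that name. But the summary does call the pairing prediction, and the word prospective gives no lead time to two measurements from one session. The panel's later rating, and the option to finish on another day after intense fatigue, do not create a planned interval either.

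A reader might infer more than the documents support:

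- **That sharing a session biases the outcome.** It need not. The assistant giving the battery and the clinical panel are blind to CG and MoCA results. The problem is timing, not contamination.
- **That the NCP plan predicts an earlier outcome from later change.** No passage proposes the 24-to-12 pair. The lists are offset by one visit, the 36-month ERP is recorded but not listed as a predictor, and hypothesis III says prospective. Lagged pairs were probably intended, so the fault is ambiguity.
- **That people already diagnosed with dementia will be recounted as later conversions.** Section 16h lets participants who progress continue with substitute consent, but nothing says they are re-entered as new cases. The at-risk set, and the reference point for conversion, reversion and decline, may be set in a statistical analysis plan (SAP) that is not shown. Their absence is not an error here. The protocol gives no conversion rate from which to size such an effect.

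**Conclusion.** The point holds for one CG pair. Change to 12 months against the 12-month outcome is concurrent, yet the Section 10 aim presents it as prediction, and hypothesis iii and objective iii include it without distinction. It is 1 of 12 CG pairs and 1 of 4 for the 12-month outcome. The other 11 are correctly ordered, so the CG prediction aim as a whole is not undermined. For NCP the finding is weaker: the wording leaves 12/12 and 24/24 open, although lagged pairs were probably meant.

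This rests on visit order alone and assumes no event rate or dropout. It does not establish that participants were free of dementia at the 3-, 6- or 9-month visits, since the panel does not rate status between baseline and 12 months. The point is worth correcting because it governs what the study may conclude. It needs a change of wording, not of design.

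**What to change.** In the Section 10 CG aim, hypotheses iii and III, and objectives iii and vii, limit prediction claims to pairs whose change visit precedes the outcome visit:

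- CG: 3, 6 and 9 months to 12, 24 and 36; 12 months to 24 and 36.
- NCP: 6 months to 12, 24 and 36; 12 months to 24 and 36; 24 months to 36.

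Report same-visit pairs (CG 12/12; NCP 12/12 and 24/24 if analysed) as concurrent detection. Use the same pairs for the MoCA comparisons in objectives iv and viii, so that both instruments are judged over the same lead time.

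This needs no new visits, participants or data. The cost is that the CG 12/12 result can no longer be counted as prediction. The model, the at-risk set and the reference point for each outcome category can be left to the SAP.
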